3.1.4 Study Duration

This study started in August 2011 in 4 European countries and was then extended to Canada. The European centres are now closed or being closed and the study will continue in Canada. Planned study end is 2022.

The duration of observation for an individual patient will be as long as any of the described IVIGs or the SCIG will be prescribed by the treating physician and until the next regularly scheduled visit of the patient after last infusion. For patients with PID or SID the observation period should last at least 12 months, if possible.

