Patients are treated with octagam®, panzyga® or cutaqui® according to the Investigator's prescription. For dosage recommendations please refer to the local octagam®, panzyga® or cutaqui® package leaflets.

Dosage and duration of treatment is at the sole discretion of the Investigator and will depend on the type and/or severity of the disease and the patient's clinical condition.

In case of SCIG home treatment the Investigator should promote compliance by instructing the patient to take cutaqui[®] exactly as prescribed and by stating that compliance is necessary for the patient's safety. The patient should be instructed to contact the Investigator if he/she is unable for any reason to administer cutaqui[®] as prescribed.

All dosages of octagam[®], panzyga[®] or cutaqui[®] that a patient received during the observation period at the study center are to be recorded on the corresponding eCRF pages. Dosages of cutaqui[®] that a patient administered during the observation period at home are to be recorded in the patient diary and will be entered into the eCRF later. It is of utter importance that all data entered into the diary are checked by the Investigator for completeness and any safety-relevant issues (including infusion site reactions) during each patient's visit to the study center.

Any drug dose adjustment and interruptions should be recorded on the corresponding eCRF page.

If, for any reason, the Investigator or the patient decide to discontinue the treatment with octagam[®], panzyga[®] or cutaqui[®], the observation period of this patient will be terminated. Efforts should be made to arrange a close-out visit. The reason(s) for termination in the eCRF is to be documented. Switching from one Octapharma Ig product to another Octapharma Ig product is possible without termination of the study but should be documented.

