### **5.2 Safety population (Safety)**

The Safety population will consist of all patients who had at least one infusion of any study drug.

The Safety population will be used for all analyses except the analysis of disposition. Patients will be included in the analysis according to the actual treatment received. As patients are allowed to change the study drug during the course of the study, treatment groups can be defined that are composed of more than one treatment depending on which patterns of treatment change will be actually observed.

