## 6 STATISTICAL CONSIDERATIONS AND ANALYSIS

### 6.1 Derived Variables

The below table provides the list of derived variables for demographic and baseline characteristics, various duration derivations and other important derivations applicable for this study.

Variables	Formula
Demographic and baseline characteristics	
Age at baseline (in years)	Year of the baseline visit – year of birth
Body mass index (BMI) (kg/m  )	Baseline weight (kg)/[height (m)]  . Round to two decimal places.
Derivation of durations	
Study day at any visit	Date of interest – date of first IVIG/SCIG infusion. One day is added if this difference is $\geq 0$
Treatment duration (in months)	(Date of last infusion with IVIG/SCIG – Date of first infusion with IVIG/SCIG + 1)/30.4375. Round to one decimal place.
Study duration (in months)	(Maximum(Date of close-out visit, date of last infusion with IVIG/SCIG) - Date of first infusion with IVIG/SCIG + 1)/30.4375. Round to one decimal place.
Derivation of exposure related measures	
Dose per infusion (g)	Infusion volume (mL) x strength where strength = 0.05 for octagam® 5% strength = 0.1 for octagam® 10% and panzyga® strength = 0.165 for cutaqui®
Dose per infusion (g/kg body weight)	Dose per infusion (g)/weight (kg), weight as measured at the respective infusion visit. Round to two decimal places.
Maximum infusion rate (mL /kg body weight/hr)	See section 7.4.2 for necessary transformations. Round to two decimal places.

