### **7.2 Patient disposition**

Patient disposition information will be summarized by treatment group and overall. The number of patients who were enrolled will be shown in the overall summary, further the number and percentage of patients who received at least one infusion with study drug, who ended the study but continued treatment with study IVIG/SCIG and who terminated treatment with study IVIG/SCIG will be presented. The primary reason for early withdrawal will also be tabulated. The number of patients treated will be used as the denominator for the percentage calculation.

A table of patient disposition will also be generated by study centre and country.

The study duration (in months) of an individual patient will be calculated as (Maximum(Date of close-out visit, date of last infusion with IVIG/SCIG) - Date of first infusion with IVIG/SCIG + 1)/30.4375 and will be summarized by treatment group and overall in the Safety population.

Patient disposition will be listed.

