### 7.5.2 Analysis of efficacy endpoint(s)

#### For patients with diagnosis PID or SID:

For each fourth infusion visit (starting with infusion visit 4) and the close-out visit the influence of the treatment with IVIG/SCIG on the frequency, intensity and duration of infections and the consumption of antibiotics since the last visit is recorded. Possible outcomes are beneficial, unchanged and unfavorable. Counts and percentages of these outcomes will be summarized by infusion visit and for the close-out visit by treatment group and overall in the Safety population. In addition, the patient's last available assessments will be summarized. These summaries will be generated for the pool of PID/SID patients and for each of the two diagnoses separately.

For each fourth infusion visit (starting with infusion visit 4) and the close-out visit the occurrence of new infectious episodes (yes/no) since the last visit is recorded. In case of the occurrence of new infectious episodes patients are asked regarding the infected area and the number of infectious episodes in this area using the following pre-specified categories:

- Serious infections of the upper respiratory tract

- Serious infections of the lower respiratory tract
- Urinary tract infections
- Bacteremia/sepsis
- Bacterial meningitis
- Osteomyelitis/septic arthritis
- Bacterial pneumonia
- Visceral abscesses
- Other infectious diseases

The number and percentage of patients with new infectious episodes since the last visit and the number and percentage of patients with new infectious episodes in each of the above categories will be summarized by infusion visit and for the close-out visit by treatment group and overall in the Safety population. In addition, this summary will be generated for the patient's last available assessment.

Further the occurrence of any infectious episodes during the course of the study, the occurrence of any infectious episodes in each of the above categories during the course of the study, the total number of infectious episodes and the total number of infectious episodes in each of the above categories will be summarized by treatment group and overall in the Safety population. These summaries will be generated for the pool of PID/SID patients and for each of the two diagnoses separately.

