As cases of bacterial pneumonia actually are always recorded as cases of serious infections of the lower respiratory tract as well, the former will not be counted in the calculation of the total number of infectious episodes.

In case that a certain type of infection has occurred but the pertaining number of infectious episodes is missing this number will be set to one.

According to the study protocol (section 3.1.4) the individual duration of the study should be at least 12 months for patients with diagnosis PID or SID. To evaluate the efficacy for patients who fulfill this condition the analyses described above will be repeated in this subgroup. To evaluate the efficacy for patients who do not fulfill this condition but are at least 6 months in the study the analysis will also be repeated for patients with a study duration of at least 6 months but less than 12 months.

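### The repeated PID/SID efficacy summaries group patients by follow-up actually achieved, which treatment outcome can influence, so they do not give a 12-month result

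*SAP*

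**What the plan says.** SAP 7.5.2 sets out the PID/SID efficacy summaries: ratings of treatment influence (beneficial, unchanged, unfavorable), infections since the last visit, and infection occurrence and totals over the whole study. The set is the Safety population, everyone with at least one infusion. SAP 5.2 states: "The Safety population will be used for all analyses except the analysis of disposition". For the ratings, SAP 7.5.2 also says "In addition, the patient's last available assessments will be summarized".

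It then cites protocol 3.1.4 for a 12-month individual duration and adds two repeats. For patients who reach 12 months: "To evaluate the efficacy for patients who fulfill this condition the analyses described above will be repeated in this subgroup". For the next band: "the analysis will also be repeated for patients with a study duration of at least 6 months but less than 12 months".

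The grouping variable is defined in SAP 6.1 and 7.2 as "Maximum(Date of close-out visit, date of last infusion with IVIG/SCIG) - Date of first infusion with IVIG/SCIG + 1)/30.4375". The protocol wording behind the 12 months is softer than the SAP's restatement: "For patients with PID or SID the observation period should last at least 12 months, if possible". Under protocol 4.1, if investigator or patient discontinues treatment for any reason, "the observation period of this patient will be terminated". Protocol 3.1.5 says the same. Switching between the sponsor's own products does not end observation.

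**The concern.** A group defined by reaching 12 months is defined by the future. Because stopping treatment closes observation, a patient who does badly, reacts badly or loses confidence can fall out of the 12-month group for that reason. The SAP presents the group as an evaluation of efficacy and gives no caution about this. Reasons for early withdrawal are tabulated in the disposition summary, but not by duration band. Patients with less than 6 months have no band of their own.

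There is a second difficulty. Follow-up in the 12-month group has no upper limit. The study began in August 2011 and was planned to end in 2022, so one-year and many-year patients can sit together. Infection occurrence and totals are accumulated over the study with no person-time denominator.

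At stake is how the 12-month figures will be read. They may be taken as what PID/SID patients can expect over a year of treatment, which this grouping does not show.

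**Working it through.** The plan gives no figure to reproduce: no sample size calculation, no test and no assumed stopping or infection rate. Every rate below is therefore an assumption, varied to show the range.

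**1. Ratings.** Let f be the share doing poorly (rated unfavorable), and let s_f and s_n be the probabilities of less than 12 months' follow-up for those doing poorly and for the others. The unfavorable share in the 12-month group is

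f(1 − s_f) / [f(1 − s_f) + (1 − f)(1 − s_n)].

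Example: f = 0.20, s_f = 0.70, s_n = 0.30 gives 0.06 / (0.06 + 0.56) = 9.7%, against 20% in the full set.

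| s_f | s_n | f = 10% | f = 20% | f = 30% |
|---|---|---|---|---|
| 0.30 | 0.30 | 10.0% | 20.0% | 30.0% |
| 0.50 | 0.30 | 7.4% | 15.2% | 23.4% |
| 0.70 | 0.30 | 4.5% | 9.7% | 15.5% |
| 0.90 | 0.30 | 1.6% | 3.4% | 5.8% |
| 0.30 | 0.50 | 13.5% | 25.9% | 37.5% |

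Equal stopping leaves the share unchanged. Earlier stopping among those doing poorly flatters the 12-month group, and the reverse pattern (last row) makes it look worse.

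**2. Cumulative infections, no selection.** At a constant rate of 1 per year, P(any infection) = 1 − exp(−time in years): 22% at 3 months, 53% at 9, 63% at 12 and 86% at 24. Mean counts are 0.25, 0.75, 1.0 and 2.0. Longer follow-up alone raises both measures.

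**3. Selection and unequal follow-up together.** Take 20% doing poorly at 3 infections per year and 80% at 1 per year. Suppose 70% of the first group and 30% of the second stop at 4 months, and all others are followed for 24 months.

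- Mean count, all patients: 0.2(0.7×1 + 0.3×6) + 0.8(0.3×0.333 + 0.7×2) = 0.50 + 1.20 = 1.70.
- Mean count, 12-month group: (0.06×6 + 0.56×2) / 0.62 = 2.39.
- Any infection: 70.1% in all patients, 87.8% in the 12-month group.
- Patient-years per patient, all: 0.2(0.7×0.333 + 0.3×2) + 0.8(0.3×0.333 + 0.7×2) = 1.37. Rate: 1.70 / 1.37 = 1.24 per patient-year.
- Rate, 12-month group: 2.39 / 2 = 1.19 per patient-year.

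The same pattern held in all 12 combinations tried (f = 10, 20 or 30%; 2 or 3 infections per year in those doing poorly; 0.5 or 1 in the others). Occurrence and mean count were higher in the 12-month group, and the rate per patient-year was lower. The planned cumulative summaries and a rate can thus point in opposite directions.

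**The case against.** The strongest reply is that these are repeats. The main PID/SID summaries keep every treated patient, including the last available ratings of those who stopped early, and patients at 6 to under 12 months have a group of their own. The SAP's wording is openly conditional on reaching 12 months. It plans no contrast between the two groups and no test, and it lists disposition and all efficacy outcomes.

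Short follow-up also need not mean failure. Protocol 3.1.4 says the European centres were closed or closing. SAP 7.2 counts patients who ended the study while continuing treatment. Intolerance of one product can lead to a switch rather than an exit. The documents give no split of reasons.

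All of this stands. A reader might infer that early stoppers are removed from the efficacy analysis and that efficacy therefore looks better. The documents do not support that: those patients remain in the Safety population results, the direction for the ratings depends on unknown stopping patterns, and cumulative infection summaries can look worse in the 12-month group.

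The reply does not reach the grouping itself, which remains post-baseline, uncapped, silent on patients under 6 months and without reasons for ending by band. The main result is also a partial safeguard only. PID/SID efficacy is recorded from infusion visit 4, at every fourth infusion visit and at close-out. A patient who stops before visit 4 contributes only through a close-out visit, which the protocol asks sites to try to arrange, and missing ratings are not imputed.

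**Conclusion.** The point holds in a limited form. The two duration groups condition on a post-baseline quantity that treatment outcome can influence, and the 12-month group does not answer a 12-month question. If patients doing poorly leave sooner than others, its ratings will look too favourable: with f = 20% and s_n = 30%, 15.2% to 3.4% unfavorable instead of 20% when 50% to 90% of them leave before 12 months. With equal leaving there is no distortion, and the reverse pattern gives 25.9%. Cumulative infection summaries are pulled upward by longer follow-up. The net direction cannot be settled from the documents.

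The weight is modest: a supplementary, descriptive repeat on the secondary objective. The primary safety objective and the main Safety population efficacy summaries are unaffected. The change is worth making because it is cheap and the 12-month figures are otherwise hard to interpret.

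**What to change.** Keep the Safety population result as the main one and say so. Then choose one of two routes.

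- **Potential follow-up.** Include all PID/SID patients whose first infusion was at least 12 months before their centre closed or before the data cut-off, whether or not they stayed. Use assessments from about the first 12 months, with early stoppers contributing until they stop. State a rule for assessment intervals that straddle month 12, because outcomes are recorded since the last visit.
- **Duration bands.** If the bands are kept, show all three (under 6, 6 to under 12, at least 12 months) side by side with the reason for ending observation. Label them as post-baseline groups and report infections per patient-year. The rate corrects for unequal follow-up, not for selection, so the reasons for ending are still needed.

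The cost is some SAP wording and extra tables. The first route also needs centre-closure dates, which are not among the eCRF contents described in protocol 3.1.3, and its cut at month 12 will be approximate. The 12-month ratings may come out less favourable. Neither route needs new patient data.

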**For patients with diagnoses different from PID or SID:**

At each infusion visit and the close-out visit patients with diagnoses other than PID or SID are asked regarding the development of the disease since the last visit. Possible outcomes are improved, not changed and deteriorated. The number and percentage of patients with these outcomes at each infusion visit and the close-out visit will be summarized by treatment group and overall in the Safety population. In addition, this summary will be generated for the patient's last available assessment.

At the close-out visit, patients with diagnoses other than PID or SID are also asked regarding the influence of IVIG/SCIG treatment on the course of the disease. Possible outcomes are beneficial, unchanged and unfavorable. The number and percentage of patients with these outcomes will be summarized by treatment group and overall in the Safety population.

These summaries will be generated for the pool of non-PID/SID patients and for each of the pre-specified diagnoses (see section 7.3.2) separately.

All efficacy outcomes will be listed.

## 7.6 Safety analysis

This section describes the safety analyses that will be conducted on the treatment period, i.e., the safety analyses on all data collected during the treatment period and all data collected in patients who dropped-out during the treatment period.

Safety analyses will be conducted on the Safety population and will be performed for all safety variables specified below.

All safety data will be summarized by treatment group and overall.

No statistical tests will be performed.

### 7.6.1 Individual Case Safety Reports (ICSRs) and Adverse Drug Reactions (ADRs)

There will be a clear differentiation between ‘cases’ and the individual symptoms reported. This distinction is reflected in the eCRF by the possibility to enter several symptoms on a single ADR form. The following terminology is used in this document to clearly reflect this differentiation:

ADR = A single symptom or term reported; always coded to an individual MedDRA preferred term (PT).

Individual Case Safety Report (ICSR) = All reported symptoms or terms that are related to one and the same infusion (except re-challenges – to be counted also as one ICSR).

The assessment of severity and relatedness to study drug will be done on the case level.

For all analyses (except the listing of ICSRs leading to death), cases recorded on the ADR form of the eCRF but rated as “not related” will be excluded. Further, cases recorded on the ADR form but with a start date before the first IVIG/SCIG infusion will be excluded from all summaries as well but will be included in the listings if not rated as “not related”.

An overview table will show the count and percentage as well as the number of ICSRs regarding the occurrence of any ICSR, any serious ICSR, and any ICSR leading to withdrawal of study drug by treatment group and overall. Percentages will be calculated with two different denominators:

- Number of patients in the respective treatment group

- Number of infusions in the respective treatment group.

This overview table will also be presented by diagnosis.

The tabulation of count and percentage of ADRs and serious ADRs will be based on PTs and SOCs of the MedDRA thesaurus. MedDRA version 23.0 will be used for coding. Percentages again will be calculated based on the number of patients and on the number of infusions by treatment group and overall.

These summaries of ADRs will also be presented by diagnosis, by country (Austria, Spain, France, UK and Canada) and by age group (age categories < 18, 18-43, 44-68, and > 68 years).

All ICSRs will be listed, in addition, there will be separate listings for

- ICSRs leading to death (this listing will also include cases rated as “not related”).
- Serious ICSRs
- ICSRs leading to withdrawal of study drug.

In summaries by SOC and PT, ADRs will be sorted by decreasing frequency in the overall group by SOC and then by PT within SOC.

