## **7 STATISTICAL METHODS**

### **7.1 General statistical conventions**

All statistical procedures will be completed using SAS version 9.4 or higher.

Continuous variables will be summarized using descriptive statistics, including number of subjects (n), mean, median, standard deviation (SD), minimum and maximum.

For categorical variables, summaries will include counts of patients and percentages. Percentages will be rounded to one decimal place.

All summaries will be presented by treatment group and overall, unless otherwise specified. As patients are allowed to change the study drug during the course of the study, treatment groups can be defined that are composed of more than one treatment depending on which patterns of treatment change will actually be observed. In case that such treatment groups are defined, summary tables by visit or summary tables for events that occur within the study will contain more than one column for these composed treatment groups. A patient will be summarized in the column that belongs to the actual treatment that the patient received at the respective visit or at the onset of the respective event.

All patient data, including those derived, will be presented in individual patient data listings. Unless otherwise stated, unscheduled visit results will be included in date/time chronological order, within patient listings only. All listings will be sorted by centre, patient number, date/time and visit (if applicable). The treatment group as well as patient's sex, age and diagnosis will be stated on each listing. Unless otherwise stated, data listings will be based on the Safety population.

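### On the likelier reading of SAP 7.6.1, re-challenge reactions are merged into one ICSR, so the per-infusion ICSR percentage understates the share of infusions with a reaction

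*SAP*

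**What the plan says.** SAP 7.6.1 separates cases from symptoms. An ADR is one reported symptom or term, coded to one preferred term. An ICSR collects all symptoms "related to one and the same infusion (except re-challenges – to be counted also as one ICSR". The term re-challenge is not explained there or anywhere else in the two documents.

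The overview table is introduced as follows: "An overview table will show the count and percentage as well as the number of ICSRs regarding the occurrence of any ICSR", with further rows for serious ICSRs and ICSRs leading to withdrawal. It has two denominators: "Number of patients in the respective treatment group" and "Number of infusions in the respective treatment group". No rule adjusts either side for re-challenges. The overview is repeated by diagnosis, and SAP 7.7.1 adds ICSR summaries by country and age group.

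The ADR tables by system organ class and preferred term use the same pair of denominators: "Percentages again will be calculated based on the number of patients and on the number of infusions by treatment group and overall". The re-challenge exception is attached to the ICSR definition only. SAP 3.4 makes the incidence of ADRs, not of ICSRs, the primary endpoint.

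**The concern.** A percentage of infusions is naturally read as the share of infusions followed by a reaction. That reading needs a numerator counted in infusions. The base ICSR definition supplies one, and the exception takes it away for re-challenges: the later infusion stays in the denominator, but its reaction no longer adds to the numerator.

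Repeated infusions are the norm for part of this population. Protocol 3.1.4 says "For patients with PID or SID the observation period should last at least 12 months, if possible". Two products with the same number of patients who react could show the same per-infusion ICSR percentage even if, with one of them, reactions come back on re-challenge. The safety analysis is purely descriptive, so these percentages are themselves the result; no test or interval exists to qualify them. Because the key term is undefined, two programmers could also produce different tables from the same data.

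**Working it through.** The plan states no reaction rate, recurrence rate or expected ICSR percentage, so it has no figure to reproduce. What can be checked is the direction of the effect and how it scales.

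**Which reading is likelier.** Under the base rule, a reaction at a later infusion is already its own ICSR. An exception that merely kept it separate would do nothing. The exception has clear work to do if it merges the later reaction into the earlier case, and I take that reading below.

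**Inputs.**
- Numerator: number of ICSRs, with re-challenges merged (SAP 7.6.1, reading above). The SAP does not pair each numerator with its denominator explicitly; I take the number of ICSRs as the one that goes with infusions.
- Denominator: all infusions in the group (SAP 7.6.1).
- Patients: 300–500 (SAP 4); 400 assumed.
- Infusions per patient: not specified (SAP 3.1); 12 assumed, giving N = 400 × 12 = 4,800.
- Reacting infusions R and merged share f: not in the documents; ranges assumed.

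**One patient.** With one first reaction and k merged re-challenge reactions in m infusions, the share of infusions with a reaction is (1 + k)/m and the ICSR percentage is 1/m, a ratio of 1/(1 + k). With m = 12 and k = 1, 2 or 3, the ICSR figure is 1/12 = 8.3% each time, against 2/12 = 16.7%, 3/12 = 25.0% or 4/12 = 33.3%.

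**A group.** The share of infusions with a reaction is R/N. The merged ICSR percentage is R(1 − f)/N. The ratio is 1 − f.

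| f | R = 240 (5.00% of infusions) | R = 48 (1.00% of infusions) |
|---|---|---|
| 0 | 5.00% | 1.00% |
| 5% | 4.75% | 0.95% |
| 10% | 4.50% | 0.90% |
| 25% | 3.75% | 0.75% |
| 50% | 2.50% | 0.50% |

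**A mixed group.** Suppose 10 patients react three times each, with the second and third reactions merged, and 30 patients react once. Reacting infusions: 10 × 3 + 30 = 60, and 60/4,800 = 1.25%. ICSRs: 10 + 30 = 40, and 40/4,800 = 0.83%. Here f = 20/60, one third. The per-patient figure is 40/400 = 10.0% either way.

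**Would trimming the denominator help?** Removing the merged infusions from it as well gives R(1 − f)/(N − Rf). At R = 240 and f = 25% this is 180/4,740 = 3.80%, against 3.75% untrimmed and 5.00% for the share of infusions with a reaction. The remedy has to be in the numerator.

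**The case against.** The strongest reply is that the wording does not establish merging. The phrase could mean that each re-challenge counts as one ICSR of its own; then f = 0 and nothing is understated. It could also mean a restart within one infusion. If that restart were its own case, one infusion could yield two ICSRs and the percentage would err upwards. These readings cannot be excluded, so merging is the likelier reading and not a stated fact.

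A reader might infer that every infusion after a first reaction is a re-challenge, so that a patient reacting at all 12 of 12 infusions counts as 1/12 = 8.3% instead of 100%. The documents do not support this. It would cancel the per-infusion rule for every recurring reaction. On a narrower reading, reactions at ordinary successive infusions remain separate ICSRs. Under Protocol 3.1.1 and 3.1.5, discontinuing treatment ends observation and the patient cannot re-enter, so re-exposure after permanent discontinuation is not observed. The merged share may therefore be small.

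A reader might also infer that the primary endpoint is understated. That is not shown: the endpoint is ADR incidence, and the exception is not attached to ADRs. What stands is that the SAP does not say how a symptom recurring at re-challenge counts in those tables.

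Finally, a reader might infer that a reaction recurring after a product switch is credited only to the first product. That is inference. SAP 7.1 says "A patient will be summarized in the column that belongs to the actual treatment that the patient received at the respective visit" and continues with the same principle for the onset of an event. Nothing says that a reaction to a second product is a re-challenge of the first, or how a merged case spanning a switch is dated.

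It is also fair to say that all ICSRs and all infusion details are listed. Listings let a reader look for recurrences but give no rate.

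**Conclusion.** The point holds in a limited form. If re-challenge reactions are merged, the per-infusion ICSR percentage lies below the share of infusions with a reaction by the factor 1 − f. The direction is certain once one such reaction is merged. The size is unknown: at an assumed 5% of infusions reacting, the table would show 4.75% at f = 5%, 3.75% at f = 25%, and 5.00% if nothing is merged.

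The effect is confined to events classed as re-challenges and to the per-infusion ICSR figures, including their subgroup versions. Per-patient percentages are unaffected, and for the ADR tables the rule is unspecified, not shown to be wrong. No test or power is involved. The rule should be corrected before the tables are programmed, but it does not put the primary endpoint in doubt.

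**What to change.** In SAP 7.6.1:

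1. Define re-challenge, and state how a recurrence counts in the ICSR tables and, separately, in the ADR tables for each denominator.
2. Keep the merged ICSR for case counts and per-patient percentages.
3. For the infusion denominator, use as numerator the number of infusions with at least one related reaction, each counted once and assigned to the product given at that infusion. This gives the same result whichever meaning of re-challenge was intended, provided the recurrences were recorded.
4. Where recurrence dates were not recorded, footnote that the percentage is a lower bound. Protocol 3.1.4 reports the European centres closed or closing, so some dates may be unrecoverable there.

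The cost is a few lines of SAP text and one derived flag per infusion, using treatment dates and products that Protocol 3.1.3 already requires to be recorded. The per-infusion percentage will come out slightly less favourable wherever reactions had been merged.
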